9.8 Detailed Analysis Plan

Prior to looking at the data and database closure, if needed, a detailed statistical analysis plan will be prepared and finalized to completely specify the statistical procedures to be applied to the data by the statistician who will conduct the analysis. The plan will amplify on the methods discussed in this protocol, will address any protocol changes that would affect the analysis, and will provide a rationale for any changes to the analysis.

10.0 Safety Monitoring

Subject safety will be monitored throughout the course of this study by monitoring for Adverse Events and Product Complaints related to the AtriClip device. The AtriClip device used during the index procedure for the clinical study has been cleared for marketing by the FDA and is being used within the current labeling and indications for use. Any event that occurs that may have caused or contributed to a death or serious injury or that indicates the AtriClip device has malfunctioned and would be likely to cause or contribute to a death or serious injury if the malfunction were to recur will be reported in compliance with 21 CRF Part 803.

In addition to general surgical risks, additional risks specifically associated with the AtriClip implant are as follows:

- Incomplete exclusion of left atrial appendage (LAA)
- Additional surgery if the device is not placed in the correct position.
- Allergic reaction to the implant materials

Study Number: CP2015-2 **CONFIDENTIAL** Page 37 of 48

- Device misplacement or embolization
- Device breakage
- Inability to move or retrieve device

There may also be other risks that are unforeseen at this time.

10.1 Adverse Events

10.1.1 Definition of an Adverse Event

Adverse Event (AE): any undesirable clinical occurrence or change from a patient's baseline (pre-index procedure) condition, whether it is device related or not.

Adverse Event Identification: a condition that is one of the following:

- a. A unique symptom or event that is a change from the subject's baseline status
- b. A series of symptoms or events that can be categorized as a single entity based on definitions found herein
- c. A specific diagnosis responsible for a clinical change
- d. A worsening or exacerbation of a pre-existing condition

10.2 Serious Adverse Events

10.2.1 Definition of a Serious Adverse Event

Serious Adverse Event (SAE): any adverse event is considered serious if it results in death, is life threatening, requires hospitalization (initial or prolonged), results in disability or permanent damage, causes congenital anomaly/birth defect, requires intervention to prevent impairment or damage, or other serious (important medical events) which may jeopardize the subject and may require medical or surgical intervention to prevent one of the above outcomes.

Note: "Death" should not be reported as an adverse event. The cause of death should be reported as an adverse event. The only exception is "Sudden Death" when the cause is unknown.

10.2.2 Subject Death

Subject death during the investigation must be reported by the Investigator (or designee) by completing the Study Exit eCRF in the database along with the cause of death. The electronic Adverse Event Form is necessary if the event was related to the AtriClip device or placement of the device. In addition, subject death must be reported to the IRB in accordance with IRB requirements.

10.2.3 Adverse Event Classification

The investigator is required to provide:

- Time interval of the event The time interval of the occurrence of the adverse event should be assessed in relationship to timing of the index procedure (AtriClip placement)
- Date of event onset and outcome of the event, or date of death
- Severity of the event (Mild, Moderate, Severe)
- Action taken for medical management of the event
- Relationship of the event it is the PIs responsibility to assess the relationship of an AE and provide primary cause. Events will be categorized by relationship to the AtriClip device, the applier, ancillary device, and the index procedure or other.

Study Number: CP2015-2 CONFIDENTIAL Page 38 of 48

Adverse events will be assessed to determine if the event meets the definition of a serious adverse
event.

10.2.4 Reporting Adverse and Serious Adverse Events

The investigator (or designee) will record all AEs (both serious and non-serious and regardless of relationship) in the source documents. The Investigator at each site participating site is responsible for reporting AEs and SAEs to AtriCure only when they are related to the LAA exclusion index procedure or device. AEs related to the LAA exclusion procedure or device will be reported on the eCRF. The CRFs allow the investigator to indicate whether or not the adverse events are related to the AtriClip device or AtriClip placement (index procedure).

- Use a separate Adverse Event Form to document each event
- The Adverse Event Form must be electronically signed by the Investigator Note: It is the responsibility of the Investigator to inform their IRB of SAEs as required by their IRB procedures and in conformance with FDA requirements.

All Serious Adverse Events that are related to the LAA exclusion index procedure or device must be reported by the Investigator by submitting the AE eCRF to AtriCure within 10 days of becoming aware of the AE and recorded on the Serious Adverse Event Source Document Collection Form An event determined by the Investigator to be life threatening or to have led to death should be reported within 24 hours.

The Investigator shall send a written report including a narrative description of the SAE to AtriCure within three (3) working days of the initial report. The Investigator should follow all unresolved SAEs until the events are resolved, or the subject has exited the study or the AE is otherwise explained.

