An Electronic Data Capture (EDC) system will be utilized by study site personnel to transfer study data from source records (medical records and/or source document worksheets) onto common electronic case report forms (eCRFs). The EDC system is a web-based, secure electronic software and is compliant with national and international GCP data protection/data privacy and electronic record/electronic signature (e.g., 21 CFR Part 11) regulatory requirements.

Serious Adverse Events (SAEs) and product quality problems (for products used during the index procedure), including potential and actual product use errors suspected to be associated with the use of a Food and Drug Administration (FDA) regulated drug, biologic, medical device or dietary supplement used during the course of this study will be reported by the PI to applicable authorities including the: 1) Sponsor (AtriCure); 2) IRB; 3) respective manufacturer(s); and/or 4) FDA via MedWatch Online Voluntary Reporting Process or Medical Device Reporting (MDR) as appropriate.

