4.0 INVESTIGATIONAL PLAN

4.1 Overall Study and Design – Subject Disposition Diagram

Study Number: CP2015-2 CONFIDENTIAL Page 18 of 48

Overall Study and Design - Description

All patients who undergo a valve or CABG (structural heart) procedure with direct visual access to the LAA will be eligible to participate based upon consent and evaluation of the inclusion and exclusion criteria defined in this protocol.

The target patient population includes patients at risk of POAF based on the CHA2DS2-VASc and HASBLED scoring.

Patient must meet all inclusion/exclusion criteria (including intra-operative exclusion criteria) before enrollment or randomization.

During the planned structural heart procedure, the intra-operative exclusion criteria will be assessed. If any intra-operative exclusion criteria are met, the subject will be a screen fail and will not be enrolled or randomized.

To execute randomization, at the time of enrollment, subjects will be assigned a sequential identification number at each site and a corresponding sealed envelope which will be opened in the operating room to reveal the treatment group. Subjects will be randomized 2:1 (2 with AtriClip® to 1 with no AtriClip®). Randomization sequences will be generated by the AtriCure Statistician and will be stratified by site. The subject population will be randomized using a blocking scheme for each surgeon to ensure equal and balanced treatment group allocations and to avoid bias with respect to known or unknown subject variables that could affect the outcome of this study.

Post-index procedure, all subjects will be monitored per the hospital standard of care processes for POAF.

Four (4) treatment arms result:

- Surgery with AtriClip (POAF diagnosed / Institution SoC anticoagulation therapy)
- Surgery with AtriClip (No POAF)
- Surgery with no AtriClip (POAF diagnosed / Institution SoC anticoagulation therapy)
- Surgery with no AtriClip (No POAF)

Subjects will be assessed for AEs related to the placement of the AtriClip and will be instructed to notify the PI of any AEs that occur during the study. All subjects that develop POAF during the hospital stay will be followed for approximately 1 year (365 days) post index procedure. In addition, all the subjects in the AtriClip group that do not develop POAF will also be followed for 365-days post index procedure.

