9.0 STATISTICAL METHODS

9.1 Clinical Study Objective

The objectives of this study are to:

- 1. Compare impact of POAF among two randomized treatment arms; patients with POAF and surgical LAA closure (using AtriClip Gillinov-Cosgrove LAA Exclusion Systems) versus patients with POAF and no surgical LAA closure.
- 2. Evaluate Healthcare resource utilization [i.e. Hospital length of stay (LOS), emergency room and/or hospital re-admissions, and costs associated with specific adverse events that may be related to atrial fibrillation].
- 3. Evaluate long-term outcomes of LAA closure with AtriClip in patients at risk of developing POAF.

These patients will be enrolled prior to a scheduled existing cardiac procedure and randomized prior to the study index procedure (AtriClip placement). Perioperative event rates and postoperative outcomes including reoperation for bleeding, hospital length of stay, neurologic consults for stroke/TIAs, ED visits, and hospital readmissions through interval follow ups will be determined.

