9.2 Study Endpoints

The following endpoints will be collected for this hypothesis generating pilot study:

- 1. Perioperative complications associated with AtriClip placement. [Defined as: stroke, major bleeding that requires re-operation and/or transfusion of > 2 U packed red blood cells (PRBC) within any 24-hour period during the first 2 days' post-index procedure, myocardial infarction (MI), or death.]
- 2. Intraoperative successful exclusion of LAA. [Defined as no (0 mm) flow between LAA and LA and < 5 mm LAA remnant by intraoperative TEE with Doppler.]
- 3. Composite event rates between the group of subjects diagnosed with POAF (AtriClip vs no AtriClip) through 365 days' post index procedure and between the group of subjects not diagnosed with POAF (AtriClip vs no AtriClip) through 30 days' post index procedure. Events to be evaluated include: Thromboembolic & Hemorrhagic Events such as cerebrovascular accident (CVA), transient ischemic attack (TIA), peripheral ischemia, hemorrhagic stroke, neurologic bleed, gastrointestinal (GI) bleeds, or other major bleeding event.
- 4. Composite event (listed above) rates through 365-days post index procedure for all AtriClip patients, regardless of whether the patient develops POAF.
- 5. Healthcare resource utilization variance between groups as related to the composite events above. [Specifically hospital length-of-stay (LOS), reoperation for bleeding, neurologic consults for stroke or TIA, emergency department (ED) visits, and hospital readmissions.]

[figure not shown]

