9.7.2 Safety Analysis

A Pearson's Chi-Squared test will be used to compare the incidence of complications associates with LAA exclusion between the two procedure groups. Alternatively, a Fisher's Exact test will be used if justified by small cell counts (less than 5) and Clopper-Pearson (Exact) 95% CI will also be reported. Thromboembolic and hemorrhagic events will be similarly analyzed.

In addition, complications associated with LAA exclusion and thromboembolic/hemorrhagic might also be analyzed using multiple logistic regression model similar to the effectiveness endpoint (successful LAA exclusion) described above.

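### Section 10.2.4 limits AE reporting to LAA-exclusion-related events, in conflict with other sections, and 9.7.2 compares such complications with a no-clip arm without naming a data source, so non-fatal events such as MI may be captured unequally

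*Combined protocol and SAP*

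**What the plan says.** **Reporting rule.** Section 10.2.4 has every AE recorded in site source documents whatever its cause. AEs and SAEs go to the sponsor "only when they are related to the LAA exclusion index procedure or device", and the next sentence puts the same limit on eCRF entry. Section 4.1 is framed similarly: "Subjects will be assessed for AEs related to the placement of the AtriClip and will be instructed to notify the PI of any AEs". Section 10.0 describes safety monitoring as "monitoring for Adverse Events and Product Complaints related to the AtriClip device". Under 10.2.3 the investigator judges relatedness, and 9.4 describes the trial as unblinded.

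**Analysis.** Section 9.7.2 uses Pearson's chi-squared test, or Fisher's exact test for cell counts below 5, to "compare the incidence of complications associates with LAA exclusion between the two procedure groups". Thromboembolic and hemorrhagic events are handled in the same way. No form or other data source is named. Endpoint 1 (3.0 and 9.2) is headed as complications associated with AtriClip placement, but is defined by stroke, major bleeding, MI or death. Section 5.2.1 leaves the control appendage intact.

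**Text pointing to wider capture.** The Study Administrative Structure section has the investigator report "Serious Adverse Events (SAEs) and product quality problems (for products used during the index procedure") to the sponsor and others as appropriate, with no clear relatedness limit. Section 5.1 defines the index procedure as placement or non-placement of the clip, whereas 10.2.3 and 10.2.4 gloss it as AtriClip placement. Section 10.2.4 also says: "The CRFs allow the investigator to indicate whether or not the adverse events are related to the AtriClip device or AtriClip placement (index procedure"). Section 9.2 states "The following endpoints will be collected for this hypothesis generating pilot study", and 9.1 says that "Perioperative event rates and postoperative outcomes including reoperation for bleeding" will be determined; neither adds a relatedness condition. Section 10.2.2 has every death entered on the Study Exit eCRF.

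**The concern.** A comparison between randomised arms is interpretable only if events are counted in the same way in both. A relatedness filter defined by the clip cannot work equally in a group that has no clip and no LAA exclusion. Read literally, the 9.7.2 label leaves controls with almost no qualifying events. Read as any-cause stroke, major bleeding, MI or death, the AE route in 10.2.4 does not supply the control data.

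Non-fatal MI is the clearest case. Deaths have their own form in both arms. Reoperation for bleeding and neurologic consults are collected as resource use (9.1, 9.2), so they partly cover bleeding and stroke. The readable text shows no such both-arm route for non-fatal MI.

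At stake is whether the perioperative safety comparison reflects the effect of adding the clip or partly reflects which sites were asked to report. In a hypothesis-generating pilot the consequence is a misleading safety signal or a missed one, not a wrong confirmatory claim.

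**Working it through.** **Passages side by side**

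| Question | Narrow reading | Wider reading |
|---|---|---|
| Which AEs reach the sponsor and eCRF? | Related only (10.2.4; similar framing in 4.1 and 10.0) | SAEs without a clear limit (Study Administrative Structure); forms record whether or not an event is related (10.2.4) |
| Can a control event be related to the index procedure? | Hardly: index procedure means AtriClip placement (10.2.3, 10.2.4) | Not barred: it includes non-placement (5.1) |
| What is endpoint 1? | Its heading: associated with placement | Its definition: events possible in either arm |
| What feeds 9.7.2? | Not stated | Not stated |

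The narrow readings together give arm-dependent capture and the wider ones do not. The plan does not say which applies.

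**Size if the narrow reading applies (illustration)**

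The plan gives no MI rate or capture share, so there is no figure of its own to reproduce on this point. Inputs:

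- From the plan: 1333 clip and 667 control subjects (9.4); the Pearson or Fisher rule (9.7.2), with Fisher applied when either arm has fewer than 5 events; two-sided 0.05 (9.7).
- Assumed: true MI 3% or 1% in both arms; share of MIs recorded 10% or 25% in the clip arm and 0% in controls; other endpoint 1 components recorded equally in both arms at 1% to 10%.

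Recorded rate = true MI × share recorded + other components.

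Example: the clip arm has 0.03 × 0.25 + 0.02 = 2.75%, and controls have 0.03 × 0 + 0.02 = 2%. Expected MIs are 1333 × 0.03 = 40.0 with the clip, of which 10.0 are recorded, and 667 × 0.03 = 20.0 in controls, of which none is recorded.

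P(false clip excess) = Σ Bin(b; 1333, r_clip) × Bin(a; 667, r_control), summed over all pairs (b, a) with p < 0.05 and b/1333 > a/667.

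True MI 3% in both arms:

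| Other components | 10% vs 0% recorded | 25% vs 0% recorded | 25% vs 25% recorded |
|---|---|---|---|
| 1% | 0.062 | 0.223 | 0.020 |
| 2% | 0.055 | 0.158 | 0.022 |
| 3% | 0.049 | 0.127 | 0.023 |
| 5% | 0.043 | 0.096 | 0.023 |
| 10% | 0.038 | 0.071 | 0.024 |

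The nominal value in this direction is 0.05 / 2 = 0.025. At 1% true MI, with 25% versus 0% recorded, the probability is 0.051, 0.048 and 0.044 for other components of 1%, 2% and 3%.

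**Loss of information.** Take other components at 2% and MIs recorded 25% versus 0%. True MI of 3% versus 3% and of 3% versus 1% both give recorded rates of 2.75% and 2%, so the probability of a significant clip excess is 0.158 in each case. With full recording, the rates are 5% versus 5% (probability 0.023) and 5% versus 3% (probability 0.561). With no control MIs recorded, the data cannot distinguish a real MI excess from none.

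**The case against.** The strongest objection is that AE reporting to the sponsor and endpoint collection are separate pathways. Section 10.2.4 governs reporting for a cleared, post-market device. Sections 9.1 and 9.2 speak of endpoints being collected and event rates determined, with no relatedness condition, and 8.1.2 has the EDC collect all study data. Nothing readable says that the endpoint 1 test draws on the AE form. The contents list includes a schedule of assessments, and several pages between 6.1 and 8.0 are not readable; a both-arm endpoint form could be there. This stands, and it is why the point is conditional.

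A second objection is that 9.8 provides, if needed, for a detailed analysis plan before database closure. That plan could name a data source, but it could not by itself restore events never entered on an eCRF; that would mean returning to source documents.

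A third is that the size rests on chosen inputs. This is also correct. At 10% capture, or at 1% MI, the inflation is small. An MI-only test at 3% MI and 25% versus 0% capture would give 0.67, but 9.7.2 does not specify such a test, so that figure should not be used as the size of the problem.

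A reader might infer that control-arm events are barred from reporting, or that the 9.7.2 comparison is already biased. The documents do not support either. Section 5.1 includes non-placement in the index procedure, the Study Administrative Structure text can be read as wider SAE reporting, and the 24-hour sentence in 10.2.4 on life-threatening or fatal events does not repeat the relatedness condition, although it follows one.

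**Conclusion.** The concern holds as a conditional one. The reporting rule in 10.2.4 conflicts with the Study Administrative Structure text and with 5.1. The comparison in 9.7.2 is labelled by something controls do not undergo, and its data source is not stated. If AE eCRF records or attribution feed it, non-fatal events, most clearly MI, would be captured unequally by arm on unblinded judgement. Deaths are not affected.

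Under the assumed 3% MI in both arms, the probability of a false significant clip excess is about 0.05 to 0.06 at 10% versus 0% capture (other components 2% down to 1%) and 0.07 to 0.22 at 25% versus 0% (other components 10% down to 1%), against about 0.02 with equal capture. At 1% MI and 25% versus 0% capture it is 0.04 to 0.05 (other components 3% down to 1%). Only the arm sizes and the test come from the plan. Unequal capture itself is not shown. The point should be fixed because the remedy is cheap and the safety signal would otherwise be hard to interpret; confidence is medium because of the unreadable pages.

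**What to change.** 1. In 10.2.4, require every endpoint 1 and endpoint 3 event to be entered on an eCRF in both arms regardless of relatedness, through the window of each comparison (for endpoint 3, 365 days for subjects with POAF and 30 days for those without). If an existing form already does this, name it in 9.7.2 as the data source instead. Endpoint 3 belongs here because 9.7.2 analyses its events in the same way.
2. In 9.7.2, define the endpoint 1 comparison as any-cause perioperative stroke, major bleeding, MI or death by randomised arm. Describe device- or placement-related complications in the clip arm only, without a between-arm test.
3. Reconcile the Study Administrative Structure text on SAEs, the definition of index procedure in 5.1, and the wording of 10.2.3 and 10.2.4.

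The cost is protocol wording and a short event list on an eCRF, or only a named data source if the form exists. Section 10.2.4 already places all AEs in source documents, so the downside is modest extra data entry and monitoring.

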11.0 PRODUCT COMPLAINTS

11.1 Medical Device Reporting and Product Complaints

All reported device observations, malfunctions or failures for AtriClip LAA products will be reported on the **Device Complaint Form** within 10 days of observation of the Product Complaint via email to ... In the event of a suspected observation or device problem, the device shall be returned to the sponsor for analysis. In addition, the **Investigational Device Observation** eCRF should be completed within 10 days of a suspected observation or device problem.

Whenever an event involving an AtriCure device is subject to reporting under that Medical Device Reporting (MDR) regulation, AtriCure shall submit to the FDA the appropriate reports required by MDR within the time frames as identified in 21 CFR Part 803. Criteria for reporting malfunctions and potentially serious injuries is based on interpretations of medical intervention, potential for serious injury, and impact of a malfunction to a device's essential functionality. AtriCure will follow - reference documents

medical device in compliance with reporting, 21 CFR Part 803 and 21 CFR Part 820: Code of Federal Regulations, Quality system Regulations.

Study Number: CP2015-2 Record: Clinical Study Protocol **Version date:** 15Feb2017/ Rev: H CONFIDENTIAL

Page 39 of 48

11.2 Source of Product Complaint Data

Means of obtaining product complaint data include review of the subject's medical records or observation by the PI and/or study staff or the CRA.

